## 9.5 Laboratory Assessments

### 9.5.1 Variables

The following treatment-emergent laboratory abnormalities will be summarized. A treatment emergent laboratory abnormality is defined as any laboratory abnormality with an onset date on or after the date of the first dose of study drug.

| Category               | Abnormality  | SDTM LBTESTCD                              | Grading System |         |
|------------------------|--|--|----------------|---------|
| Hematology      | WBC increased                                      | WBC  | CTCAE          |         |
|                        | WBC decreased                                      | WBC  | CTCAE          |         |
|                        | ANC decreased                                      | NEUT                                       | CTCAE          |         |
|                        | Lymphocytes increased
Lymphocytes decreased     | LYM  | CTCAE          |         |
|                        | Platelets decreased                                | PLAT                                       | CTCAE          |         |
|                        | Hemoglobin increased
Hemoglobin decreased       | HGB  | CTCAE          |         |
| Serum chemistry | Albumin decreased                                  | ALB  | CTCAE          |         |
|                        | ALP increased                                      | ALP  | CTCAE          |         |
|                        | Amylase increased                                  | AMYLASE                                    | CTCAE          |         |
|                        | ALT increased                                      | ALT  | CTCAE          |         |
|                        | AST increased                                      | AST  | CTCAE          |         |
|                        | Calcium, corr increased
Calcium, corr decreased | CACORR                                     | CTCAE          |         |
|                        |  |  |                |         |
|                        |  | Creatinine increased                       | CREAT          | CTCAE   |
|                        |  | GGT increased                              | GGT            | CTCAE   |
|                        |  | Glucose increased
Glucose decreased     | GLUC           | CTCAE   |
|                        |  | LDH increased                              | LDH            | Sponsor |
|                        |  | Lipase increased                           | LIPASE         | CTCAE   |
|                        |  | Magnesium increased
Magnesium decreased | MG             | CTCAE   |
|                        |  | Phosphate decrease                         | PHOS           | CTCAE   |
|                        | Potassium increased                                | K  | CTCAE          |         |

| Category                   | Abnormality                           | SDTM LBTESTCD | Grading System |
|----------------------------|---------------------------------------|---------------|----------------|
|                            | Potassium decreased                   |               |                |
|                            | Sodium increased                      |               |                |
|                            | Sodium decreased                      | NA            | CTCAE          |
|                            | Total bilirubin increased             | BILI          | CTCAE          |
|                            | Uric acid increased       | CYURIAC       | CTCAE          |
| Urine chemistry            | UPCR increased                        | PROTCRT       | Sponsor        |
| Endocrinology  | Thyroid Stimulating Hormone increased |               |                |
|                            | Thyroid Stimulating Hormone decreased | TSH           | HLN            |

 TSH is held in the SDTM "chemistry" laboratory category; will use HLN = high, low, normal classification based on normal range

 Uric acid increases will be graded only as Grade 1 or Grade 4. Grade 2 is not defined per CTCAE v4 and Grade 3 cannot be distinguished from Grade 1 based upon the result alone.

Sponsor-defined grades are to be applied to the following analytes:

#### LDH

- Grade 1 if >ULN to ≤ 2xULN
- Grade 2 if >2xULN to ≤ 3xULN
- Grade 3 if >3xULN

#### UPCR

- Grade 1 if ≥ 17.0 to ≤ 121.0 mg/mmol (≥0.15 to ≤1.0 mg/mg)
- Grade 2 if >121.0 to ≤ 396.0 mg/mmol (>1.0 to <3.5 mg/mg)
- Grade 3 if >396.0 mg/mmol (>3.5 mg/mg)

### 9.5.2 Analysis

All laboratory data parameters and visits will include flags for values above or below laboratory reference ranges. Toxicity grades will be assigned programmatically by applying the CTCAE v 5 guidelines. Only results with assessment dates through the end of the safety observation period (see Section 4.6) will be tabulated in summary tables for the Safety and O-Safety populations.

Laboratory summaries will be presented in SI units. Continuous laboratory test results will be summarized by treatment group using descriptive statistics for actual values and for changes from baseline by scheduled visit. For test results which are below or above the quantification level, the imputed values as described in Appendix C will be used for deriving the grade and then summarized. Line graphs for mean change from baseline ± standard deviation will also be presented at each scheduled visit (with visits shown on x-axis) for the following laboratory parameters.

- Renal function

- Blood urea nitrogen (BUN)
- Creatinine
- Liver function panel
  - Total bilirubin
  - ALT
  - AST

Tables summarizing the incidence of laboratory abnormalities by baseline and maximum post-baseline CTCAE grade over all records will be presented. In addition, the following summaries will also be presented:

A] Liver function abnormalities will be assessed as follows:

- Shift from baseline based on normal ranges
- Summaries of subjects meeting Hy’s Law laboratory screening criteria as shown below:
  - $>3\times$  ULN (ALT or AST),  $>2\times$  ULN Total Bilirubin, and  $<2\times$  ULN ALP
  - $>3\times$  ULN (ALT or AST),  $>2\times$  ULN Total Bilirubin, and  $\geq 2\times$  ULN ALP
  - $>3\times$  ULN (ALT or AST),  $>2\times$  ULN Total Bilirubin, and missing ALP

B] For renal failure surveillance, a summary of subjects meeting renal failure laboratory screening criteria as shown below will be provided:

- Serum creatinine  $\geq 3.0\times$ ULN and  $\geq 2.0\times$  baseline value or
- $eGFR \leq 50\%$  of the baseline value or
- $eGFR < 30$  mL/min/1.73 m^2 and  $\geq 25\%$  reduction from the baseline value  

$$eGFR = 186 \times (\text{Creatinine in mmol per L} / 88.4)^{-1.154} \times (\text{Age})^{-0.203} \times (0.742 \text{ if female}) \times (1.210 \text{ if black})$$
 [from the UK CKD eGuide on the Renal Association website: <http://egfrcalc.renal.org/>]

C] Categorical summaries for baseline status for TSH and Free T4 will be presented. In addition categorical summaries for post-baseline TSH and Free T4 status among subjects with TSH and Free T4 in the normal range at baseline will also be presented.

For descriptive summaries for change from baseline analyses, only central lab results will be considered. For analyses of shift in grade from baseline or worst grade after baseline, all available results will be considered regardless of whether from the central or local lab.

| Summary Type                                       | Include central lab results? | Include local lab results? |
|--|------------------------------|----------------------------|
| Subject-Incidence of Treatment Emergent Laboratory | Y                            | Y                          |

| Summary Type   | Include central lab results? | Include local lab results? |
|---|-------------------------------------|-----------------------------------|
| Abnormalities in Selected Laboratory Tests by CTCAE Grade   |                                     |                                   |
| Change from Baseline in Laboratory Values   | Y                                   | N                                 |
| Shift from Baseline in Laboratory Values by CTCAE Grade   | Y                                   | Y                                 |
| Shift from Baseline in Laboratory Values by High/Low/Normal   | Y                                   | Y                                 |
| Shift from Baseline in Laboratory Values by Sponsor-defined Grades  | Y                                   | Y                                 |
| Subject-Incidence of Laboratory Abnormalities with a Between-Arm Difference of $\geq 5\%$ (All Grades) or $\geq 2\%$ (Grades 3-4) | Y                                   | Y                                 |

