**Table 5-2: Estimation of the Creatinine Clearance by Cockcroft and Gault**

|  |
|--|
| 
Serum creatinine in conventional units (mg/dL)
 

• Males: <math>(140 - \text{age}) \times \text{weight (kg)} / (\text{serum creatinine} \times 72)</math>

• Females: <math>[(140 - \text{age}) \times \text{weight (kg)} / (\text{serum creatinine} \times 72)] \times 0.85</math>

        |
| 
Serum creatinine in SI units (<math>\mu\text{mol/L}</math>)
 

• Males: <math>[(140 - \text{age}) \times \text{weight (kg)} / (\text{serum creatinine})] \times 1.23</math>

• Females: <math>[(140 - \text{age}) \times \text{weight (kg)} / (\text{serum creatinine})] \times 1.04</math>

 |

Abnormalities in any clinical laboratory test (including tests not required per protocol) that leads to a change in subject management (eg, dose interrupted or reduced, treatment discontinued, requirement for additional medication or monitoring) are considered clinically significant for the purposes of this study and should be reported as AEs. If laboratory values constitute part of an event that meets criteria defining it as serious, the event (with associated laboratory values) needs to be reported as an SAE (see Section 8.2). In cases of discordance on AE grading between duplicate local and central labs, the lab abnormality with the higher grade should be referenced for AE reporting purposes.

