### 7.1.2.1 Potential Drug Interactions with Cabozantinib

Cytochrome P450 (CYP): Data from a clinical drug interaction study (Study XL184-008) show that clinically relevant steady-state concentrations of cabozantinib appear to have no marked effect on the AUC of co-administered rosiglitazone, a CYP2C8 substrate. Therefore, cabozantinib is not anticipated to markedly inhibit CYP2C8 in the clinic, and by inference, is not anticipated to markedly inhibit other CYP450 isozymes that have lower [I]/Ki values compared with CYP2C8 (ie, CYP2C9, CYP2C19, CYP2D6, CYP1A2, and CYP3A4). In vitro data indicate that cabozantinib is unlikely to induce CYP enzymes, except for possible induction of CYP1A1 at high cabozantinib concentrations (30 μM).

Cabozantinib is a CYP3A4 substrate and a weak substrate for CYP2C9 (but not a CYP2D6, CYP2C8, CYP2C19, CYP2B6, or CYP1A2 substrate), based on data from in vitro studies. Results from a clinical pharmacology study, XL184-006, showed that concurrent administration of cabozantinib with the strong CYP3A4 inducer, rifampin, resulted in an approximately 77% reduction in cabozantinib exposure (AUC values) after a single dose of cabozantinib in healthy volunteers. Co-administration of cabozantinib with strong inducers of the CYP3A4 family (eg, dexamethasone, phenytoin, carbamazepine, rifampin, rifabutin, rifapentin, phenobarbital, and St. John's Wort) may significantly decrease cabozantinib concentrations. The chronic use of strong CYP3A4 inducers should be avoided. Other drugs that induce CYP3A4 should be used with caution because these drugs have the potential to decrease exposure (AUC) to cabozantinib. Selection of alternate concomitant medications with no or minimal CYP3A4 enzyme induction potential is recommended.

Caution must be used when discontinuing treatment with a strong CYP3A4 inducer in a subject who has been concurrently receiving a stable dose of cabozantinib, as this could significantly increase the exposure to cabozantinib.

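### Minor correction, descriptive tables only: the SAP's UPCR Grade 1/2 boundary (121.0 mg/mmol) and BMI factor (1000) are wrong as printed, and its eGFR creatinine unit should be checked against the original page

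*Combined protocol and SAP*

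**What the plan says.** **UPCR grades (SAP 9.5.1).** The section introduces its own grading with "Sponsor-defined grades are to be applied to the following analytes" and prints each UPCR limit in two unit systems. The first line reads "Grade 1 if ≥ 17.0 to ≤ 121.0 mg/mmol (≥0.15 to ≤1.0 mg/mg" (closing bracket omitted here). The second begins "Grade 2 if >121.0 to ≤ 396.0 mg/mmol" and pairs that range with values above 1.0 and below 3.5 mg/mg. SAP 9.5.2 adds "Laboratory summaries will be presented in SI units", and its table of planned laboratory outputs includes "Shift from Baseline in Laboratory Values by Sponsor-defined Grades".

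The protocol converts the same limits differently. Table 6-8 pairs 1 mg/mg with 113.1 mg/mmol and 3.5 mg/mg with 395.9 mg/mmol. The eligibility criterion on UPCR (protocol 4.2, repeated for crossover in Appendix B) pairs 1 mg/mg with 113.2 mg/mmol.

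**BMI (SAP 5.3, part C).** BMI is stated in kg per square metre and computed as weight in kg times 1000, divided by the square of height in cm.

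**eGFR (SAP 9.5.2, renal failure surveillance).** The formula divides "Creatinine in mmol per L" by 88.4 and raises the result to the power -1.154. Three alternative criteria follow:
- creatinine at least 3 times ULN and at least twice baseline;
- eGFR at or below half of baseline;
- eGFR below 30 mL/min/1.73 m² with a fall of at least 25% from baseline.

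The protocol's Table 5-2 gives a block headed "Serum creatinine in SI units", and the unit there is micromol/L.

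**The concern.** These lines are programming specifications, and a programmer who follows them literally reproduces whatever they say.

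The UPCR item matters most, because its error would pass unnoticed. A boundary 7% too high moves a narrow band of results down one grade and leaves a plausible table. Proteinuria is a recognised effect of the drug and one of the events to monitor in SAP Appendix F, so the shift table is likely to be read.

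The BMI formula gives impossible values for every subject.

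The eGFR unit, if it is as the text shows, would disable the only renal criterion that picks up a decline of 25% to 50% ending below 30.

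**Working it through.** **1. UPCR boundary**

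Inputs are the paired limits in SAP 9.5.1 and the protocol. Dividing mg/mmol by mg/mg gives the conversion factor that each pair implies:

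| Source | Calculation | mg/mmol per mg/mg |
|---|---|---|
| SAP, lower limit of Grade 1 | 17.0 / 0.15 | 113.3 |
| SAP, Grade 2/3 limit | 396.0 / 3.5 | 113.1 |
| SAP, factor 88.4 in the eGFR formula (1 mg/dL = 10 mg/L = 0.0884 mmol/L) | 10 / 0.0884 | 113.1 |
| Protocol Table 6-8, 1 mg/mg | 113.1 / 1 | 113.1 |
| Protocol Table 6-8, 3.5 mg/mg | 395.9 / 3.5 | 113.1 |
| Protocol eligibility | 113.2 / 1 | 113.2 |
| **SAP, Grade 1/2 limit** | **121.0 / 1.0** | **121.0** |

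With 113.1, the SAP's other two limits reproduce: 0.15 × 113.1 = 16.97 (printed 17.0) and 3.5 × 113.1 = 395.85 (printed 396.0). The Grade 1/2 limit does not: 1.0 × 113.1 = 113.1, against 121.0 printed. The excess is 121.0 / 113.1 = 1.07, so the SI boundary sits at 1.07 mg/mg. Using 113.2 instead also gives 1.07.

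A result above about 113.1 and up to 121.0 mg/mmol is therefore Grade 1 by the SI limit and Grade 2 by the mg/mg limit on the same line.

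**2. BMI**

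Height in metres is cm/100, so BMI = kg / (cm/100)² = kg × 10,000 / cm². For an illustrative 70 kg and 170 cm:
- as printed: 70 × 1000 / 28,900 = 2.42
- with 10,000: 70 × 10,000 / 28,900 = 24.22

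The ratio is exactly 10 for every subject.

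**3. eGFR unit**

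The meaning of 88.4 can be checked from the two forms of Cockcroft-Gault in protocol Table 5-2. The mg/dL form divides by 72 (times 0.85 for women); the micromol/L form multiplies by 1.23 (men) or 1.04 (women). Equating them gives the micromol/L equal to 1 mg/dL:
- men: 72 × 1.23 = 88.6
- women: 72 × 1.04 / 0.85 = 88.1

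So 88.4 is the micromol/L to mg/dL factor. If creatinine were entered in mmol/L, it would be 1000 times too small and eGFR would be too large by 1000^1.154 = 2,897 at every value.

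Illustration (a 63-year-old non-black woman, creatinine rising from 110 to 165 micromol/L), with eGFR = 186 × (c/88.4)^-1.154 × 63^-0.203 × 0.742:
- c in micromol/L: 46.2 falls to 29.0, a 37% fall; the third criterion is met
- c in mmol/L: 133,995 falls to 83,923, the same 37% fall, but nowhere near 30; the criterion is not met

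For her, eGFR reaches 30 at c = 160. That is 160 micromol/L when read correctly and 160 mmol/L as printed, which no subject can reach.

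The other two criteria do not depend on the unit. One uses creatinine directly. The other is a ratio, and doubling creatinine multiplies eGFR by 0.449 in either unit. They would not catch this example: halving eGFR takes a 2^(1/1.154) = 1.82-fold creatinine rise, the creatinine criterion needs at least 2-fold, and hers is 1.5-fold. A 25% fall takes (1/0.75)^(1/1.154) = 1.28-fold, so the rises at risk of being missed are those of about 1.28- to 1.82-fold that end below 30.

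**The case against.** The strongest objection concerns the eGFR item. The text was extracted from PDF, and a mu dropped from micromol could leave what is shown. The mu does survive in the protocol, in Table 5-2 and in 7.1.2.1 just after "possible induction of CYP1A1 at high cabozantinib concentrations", but the SAP is a separate document and its extracted text contains no mu at all. Other Greek letters survive in SAP 8.1.2.6, so loss is not shown either. The point is undetermined. A reader might infer that the SAP has a proven 2,900-fold error, or that renal surveillance as a whole fails. The documents support neither: the unit is uncertain, two of the three criteria work regardless, and creatinine is also graded and plotted separately.

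Next, the eGFR and BMI errors would show themselves. An eGFR above 80,000 or a BMI of 2.4 would be noticed, and SAP 11 provides for a data review meeting before lock or extraction. BMI is neither a stratification factor nor a subgroup. This stands, and it makes both items small.

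On UPCR, SAP 9.5.2 says that results are presented in SI units, not that grades are derived from the SI limits. If the mg/mg limits are programmed, nothing goes wrong. The band is also narrow. Both points stand, but the two limits on one line still disagree, and the SAP does not say which governs.

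**Conclusion.** The UPCR boundary and the BMI factor are wrong as printed. The UPCR error is about 7% and affects results of about 113 to 121 mg/mmol, provided that the SI limits are the ones programmed. The documents do not show how many results fall in that band. The BMI error is exactly 10-fold. The eGFR item is conditional: if the original page reads mmol, the inflation is 2,897-fold and the absolute criterion cannot be met; if a mu was lost in extraction, there is no error.

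A reader might take the UPCR error to reach dose management or the reporting of proteinuria as an adverse event. It does not: protocol Table 6-8 uses its own limit of 113.1, and the events to monitor are built from adverse event terms. All three items feed descriptive tables, and SAP 9 plans no formal safety comparison. ORR, PFS, alpha, power and sample size are untouched. This is a minor correction.

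**What to change.** - **SAP 9.5.1:** replace 121.0 with 113.1 mg/mmol in both the Grade 1 and the Grade 2 line. This agrees with the SAP's own 17.0 and 396.0 and with protocol Table 6-8. The 113.2 in the eligibility criterion is a rounding difference with no practical effect here.
- **SAP 5.3:** change the BMI factor from 1000 to 10,000.
- **SAP 9.5.2:** look at the original page. If it reads micromol/L, do nothing; if it reads mmol/L, change it to micromol/L.

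The cost is a few words and no new data. SAP 4.9 already lets minor corrections be made by a sponsor-approved addendum before unblinding.

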similar to that of other VEGFR-targeted therapies in DTC subjects, with manageable AEs during treatment. Table 1-2 provides a summary of AEs reported in  $\geq 10\%$  of subjects, including laboratory AEs that were deemed possibly, probably, or definitely associated with cabozantinib. The most frequent Grade 3 AEs ( $\geq 5\%$ ) were fatigue (12%), weight loss (12%), diarrhea, and palmar-plantar erythrodysesthesia (PPE; each 8%). In addition, an increase in TSH level (1.1-8.6 mIU/L) was observed in 6 subjects (at baseline all subjects were on LT4 for postsurgical hypothyroidism, and 24 had suppressed TSH). The most frequent Grade 3 laboratory abnormalities were hypophosphatemia (16%), lipase or amylase increased (12%), neutropenia (12%), and hypokalemia (8%).

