## 4 STUDY POPULATION

### 4.1 Target Population

This study will enroll subjects with RAI-refractory DTC who have progressed after prior VEGFR-targeted therapy. Eligibility criteria for this study have been carefully considered to ensure the safety of the study subjects and to safeguard the integrity of the study results. It is imperative that subjects fully meet all inclusion criteria and none of the exclusion criteria. The Sponsor will not grant waivers to study eligibility criteria.

Study eligibility criteria for all subjects are below (eligibility criteria for subjects in the placebo arm who opt to crossover to receive cabozantinib are in Appendix B):

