  - e. Bilirubin  $\leq 1.5 \times$  the ULN. For subjects with known Gilbert's disease  $\leq 3 \times$  ULN
  - f. Serum creatinine  $\leq 2.0 \times$  ULN or calculated creatinine clearance  $\geq 30 \text{ mL/min}$  ( $\geq 0.5 \text{ mL/sec}$ ) using the Cockcroft-Gault (see Table 5-2 for Cockcroft-Gault formula).
  - g. Urine protein/creatinine ratio (UPCR)  $\leq 1 \text{ mg/mg}$  ( $\leq 113.2 \text{ mg/mmol}$ )
10. Must be receiving thyroxine suppression therapy, and TSH must be below the lower cutoff of the reference range or less than  $0.50 \text{ mIU/L}$  ( $< 0.50 \text{ } \mu\text{IU/mL}$ ), whichever is lower, within 28 days before randomization.  
*(Note: If hormone replacement therapy is tolerated a TSH level of  $\leq 0.1 \text{ mIU/L}$  should be targeted.)*
11. Capable of understanding and complying with the protocol requirements and signed informed consent (or informed assent and parental/guardian consent for subjects  $< 18$  years of age)
12. Sexually active fertile subjects and their partners must agree to use highly effective methods of contraception that alone or in combination result in a failure rate of less than 1% per year when used consistently and correctly during the course of the study and for 4 months after the last dose of study treatment. For females, such methods include combined hormonal contraception (oral, intravaginal, dermal), progestogen-only hormonal contraception associated with inhibition of ovulation (oral, injectable hormonal contraception, implantable hormonal contraception), placement of an intrauterine device, or placement of an intrauterine hormone-releasing system. Males must agree to use a barrier method (eg, condom) unless they have had a vasectomy.

13. Female subjects of childbearing potential must not be pregnant at screening. Female subjects are considered to be of childbearing potential unless one of the following criteria is met: permanent sterilization (hysterectomy, bilateral salpingectomy, or bilateral oophorectomy) or documented postmenopausal status (defined as 12 months of amenorrhea in a woman over 45 years-of-age in the absence of other biological or physiological causes. In addition, females under 55 years-of-age must have a serum follicle stimulating hormone (FSH) level > 40 mIU/mL to confirm menopause). Note: Documentation may include review of medical records, medical examination, or medical history interview by study site staff.

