| Survival, post-study treatment
(Sections 5.4 and 5.7.11) |  |  |          |      |      |      |                                      |  | Subjects will be contacted every 12 weeks (± 7 days) after follow-up visit until death |

BIRC, blinded independent radiology committee; CAPN, chest/abdomen/pelvis/neck; CRF, case report form; CT, computed tomography; CTC, circulating tumor cell; ctDNA, circulating DNA; ECG, electrocardiogram; ECOG, Eastern Cooperative Oncology Group; HRQOL, health-related quality of life; IRB/EC, Institutional Review Board/Ethics Committee; MRI, magnetic resonance imaging; PK, pharmacokinetics; PT/INR, prothrombin time/international normalized ratio; PTT, partial thromboplastin time; RECIST, Response Evaluation Criteria in Solid Tumors; UPCR, urine protein/creatinine ratio.

a Results of screening assessments must be reviewed before randomization to confirm that the subject meets the eligibility criteria.

b Informed consent may be obtained greater than 28 days prior to randomization, but must be provided before any study-specific procedures are performed; however evaluations performed as part of routine care prior to informed consent can be utilized as screening evaluations if permitted by the site's IRB/EC policies.

c Additional ECGs should be performed if clinically indicated.

d This assessment is intended to confirm suitability for treatment after randomization. If this assessment has been performed during screening within 10 days (7 days for pregnancy test, 14 days for physical examination and 12-lead ECG, and 28 days for thyroid function test) prior to first dose (W1D1), this assessment does not need to be performed on W1D1 unless the subject's clinical status has changed (eg, onset of new symptoms indicative of clinical deterioration). If the assessment is performed on W1D1, the results must be available to and reviewed by the Investigator prior to any treatment being administered.

e See Section 5.7.5 and the Laboratory Manual for more detailed information on laboratory assessments.

f Thyroglobulin data will not be shared with the Investigator.

g For women under the age of 55 years to confirm menopause as needed.

h Available tumor tissue (most recently acquired before subject enrollment in the study will be obtained during screening or at enrollment.

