#### 4.2 Definition of Baseline

In general, for efficacy endpoints the last observed measurement prior to randomization will be considered the baseline measurement. Exception to this rule are efficacy biomarkers such

as pharmacogenetics blood samples, biomarker samples, bone marker samples and blood samples for potential circulating tumor cell (CTC) analyses. These samples per schedule of assessment were collected after randomization but prior to the Dose Day 1 (see definition Table 4 above), hence the baseline measurements will be with respect to this date. For subjects who did not take any study treatment, any biomarker sample available prior to randomization will be considered as baseline observation.

For safety endpoints the last observation before Dose Day 1 will be considered the baseline measurement unless otherwise specified. For assessments on Dose Day 1 where time is not captured, a nominal pre-dose indicator, if available, will serve as sufficient evidence that the assessment occurred prior to Dose Day 1.

Assessments on Dose Day 1 where neither time nor a nominal pre-dose indicator are captured will be considered prior to Dose Day 1 if such procedures are required by the protocol to be conducted before first dose.

For placebo subjects who crossover to receive cabozantinib, the second baseline will be defined as the last date of observation prior to the first date of open-label cabozantinib.

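### The SAP 9.5.2 item C table of post-baseline TSH and free T4 covers only subjects with normal baseline values, a group that inclusion criterion 10 leaves essentially empty

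*Combined protocol and SAP*

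**What the plan says.** SAP 9.5.2 item C has two parts. Baseline TSH and free T4 status is summarized without restriction. The post-baseline part is restricted: "categorical summaries for post-baseline TSH and Free T4 status among subjects with TSH and Free T4 in the normal range at baseline".

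Protocol 4.2, inclusion criterion 10, reads "Must be receiving thyroxine suppression therapy, and TSH must be below the lower cutoff of the reference range or less than" 0.50 mIU/L, "whichever is lower, within 28 days before randomization". Protocol 4.1 adds: "The Sponsor will not grant waivers to study eligibility criteria". Protocol Appendix B applies the same TSH limit again at crossover.

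On baseline, SAP 4.2 states: "For safety endpoints the last observation before Dose Day 1 will be considered the baseline measurement unless otherwise specified". Under footnote d of Protocol Appendix A, the thyroid test need not be repeated at W1D1 if it was done within the window before first dose ("28 days for thyroid function test") and clinical status is unchanged.

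Other planned outputs also cover TSH:
- SAP 9.5.1 lists TSH increased and TSH decreased, classified high/low/normal by the reference range.
- SAP 9.5.2 plans a high/low/normal shift table with no restriction on baseline status.
- SAP 9.5.2 also plans descriptive statistics for actual values and change from baseline by visit.
- SAP 5.6 groups TSH at 0.1 and 0.5 mIU/L, at baseline only.

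**The concern.** All subjects are on TSH-suppressive thyroxine, so the useful thyroid question is how often TSH rises out of suppression on study treatment. Protocol 1.3 presents TSH lowering as part of disease control. Protocol 6.7.1 lists hypothyroidism among the laboratory-related adverse events seen in at least 5% of cabozantinib-treated subjects. In the Phase 2 study NCT01811212, "an increase in TSH level (1.1-8.6 mIU/L) was observed in 6 subjects" out of 25.

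Item C is the one post-baseline summary written specifically for thyroid function. It selects subjects who start in the normal range. That wording suits a population with normal thyroid function at entry; here it selects the subjects whom the protocol excludes. If run as written, the table would be close to blank, although thyroid function is measured at W3, W5 and W9 and then every 8 weeks.

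**Working it through.** The plan gives no figure to reproduce, so the check compares two definitions.

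**1. Do the two groups overlap?** Let LLN be the lower reference limit for TSH.
- Eligible (criterion 10): TSH < min(LLN, 0.50).
- Normal at baseline for TSH (item C): TSH ≥ LLN, and not above the upper limit.
- Because min(LLN, 0.50) ≤ LLN, any TSH that satisfies the first condition fails the second, whatever the LLN.

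The documents give no LLN. A grid with LLN from 0.10 to 1.00 mIU/L (assumed) and TSH from 0.001 to 5 mIU/L gave 37,209 points that meet criterion 10. Of these, 0 were in the normal range.

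**2. Who can still enter the item C group?** Criterion 10 applies at screening, while safety baseline is the last value before first dose. A normal baseline is therefore possible in three ways:
- an eligibility deviation;
- a retest between screening and first dose, because clinical status changed or the window lapsed. A test 28 days before randomization with first dose 3 days after it is 28 + 3 = 31 days old, beyond the 28-day window. Protocol 5.7.5 gives 10 days for laboratory tests generally, so retests are more common if that text governs;
- a local versus central laboratory difference, since Protocol 5.7.5 allows local results for eligibility in some cases.

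If such exceptions are 0% to 5% of subjects (assumed), the group is:
- all subjects: 0 to 0.05 × 300 = 15;
- cabozantinib: 0 to 0.05 × 200 = 10;
- placebo: 0 to 0.05 × 100 = 5.

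In NCT01811212, 24 of 25 subjects had suppressed TSH at baseline, so 1/25 = 4% did not (Clopper-Pearson 95% CI 0.1% to 20.4%).

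**3. What do the other outputs show?**
- Low to normal or low to high: counted in the high/low/normal shift table.
- Rise above the upper limit: also counted as TSH increased under SAP 9.5.1.
- Average movement: shown by the visit summaries, though these do not give the proportion of subjects who lose suppression.
- A rise across 0.1 mIU/L that stays below the LLN: low to low in the shift table, so not shown.
- A rise across 0.5 mIU/L: not separately tabulated unless 0.5 happens to be the reference limit.

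**4. Context from Phase 2.** A TSH rise in 6/25 = 24% (95% CI 9.4% to 45.1%) corresponds to 0.24 × 200 = 48 of 200 cabozantinib subjects, with a range of about 0.094 × 200 = 19 to 0.451 × 200 = 90. At least 6 − 1 = 5 of the six started suppressed, because only one of the 25 did not. This shows that the question is a real one; it is not a count of events that the SAP would miss.

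**The case against.** The strongest reply is that the harm is mostly handled elsewhere. Item C supplements the general laboratory tables. Since nearly everyone starts low, the low-to-normal and low-to-high cells of the shift table count the subjects who leave the low range. If the Phase 2 values of 1.1 to 8.6 mIU/L are levels reached, each lies above every LLN in the assumed grid and would appear there as normal or high. A TSH change that alters management is also reportable as an adverse event (Protocol 5.7.5 and 8.1.1). This stands. A reader might infer that loss of suppression is summarized nowhere, or that about 48 of 200 events would go unseen; the documents support neither.

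A reader might also infer that the item C group can hold only protocol deviations. That is too strong, because a compliant subject can have a normal value on a retest before first dose or from a different laboratory.

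Item C could also be read separately by analyte. No eligibility criterion limits free T4, so a free T4 part could be well populated. The TSH part would still be nearly empty.

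Finally, no text commits the sponsor to post-baseline analysis at 0.1 and 0.5 mIU/L. The 0.1 level is a treatment target in a note, and 0.50 is an eligibility limit. Tabulating at these cut-offs is therefore a recommendation rather than the repair of a broken commitment. The Phase 2 rate is also weak evidence: it comes from a small single-arm study, and the text leaves open whether 1.1 to 8.6 is the level reached or the size of the rise.

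**Conclusion.** The point holds for the item C table. Its TSH denominator excludes every subject who meets criterion 10 at screening, so only exceptions can fill it: 0 to 15 of 300 if exceptions run from 0% to 5%. The disjointness does not depend on the laboratory's reference limit. The count of exceptions is an assumption.

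The consequence is small. Movement out of the low range remains visible in the high/low/normal shift table and the change-from-baseline summaries. The gap is post-baseline movement across 0.1 and 0.5 mIU/L, the cut-offs by which the SAP itself describes baseline. All safety analyses are descriptive, so no primary conclusion is affected. The change is desirable rather than essential.

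**What to change.** In SAP 9.5.2 item C, delete the normal-at-baseline restriction. For all treated subjects, including those suppressed at baseline, tabulate worst (highest) post-baseline TSH by arm and by baseline TSH category, with free T4 status alongside. Use four mutually exclusive categories in mIU/L:
- ≤0.1
- >0.1 to <0.5
- ≥0.5 to ULN
- >ULN

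The first two follow SAP 5.6, with the value 0.1 assigned to one category only; splitting at the ULN keeps values of 0.5 or more from being counted twice. The same layout can serve the crossover summaries, where the TSH entry limit is the same.

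The cost is one sentence in the SAP and one re-specified descriptive table. It needs no new data, no alpha and no change to treatment or eligibility.
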